5.0 Study Design

This is an acute, prospective, randomized, two-arm, feasibility study (Figure 2) comparing the FT-SW to FT.

[figure not shown]

Figure 2. Study Design

5.1 Endpoints

To compare the effects of FT to FT-SW in BCRL patients after one treatment based upon:

- Lymphatic activation in the affected and contralateral limb using the investigational technique of near infrared-fluorescent (NIRF) imaging
- Swelling in the affected and contralateral limb as assessed using:
 - Perometry (LymphaTech 3D Scanner)
 - Local tissue water content (MoistureMeterD)
- Skin changes on the affected and contralateral limb as assessed by:
 - Skin thickness (Ultrasound)
- Safety

Table 1. Outcome Measures

Endpoint	Outcome Measure
Lymphatic activation	
 Proportion of subjects who show an increase in the number of functional vessels and/or area of dermal backflow per NIRF imaging of the affected and contralateral arm when comparing post-treatment values to pre-treatment values Proportion of subjects who show an increase of lymphatic propulsion events immediately after treatment
Changes in Swelling	
 Proportion of subjects who show a decrease in arm perometry (limb volume) when comparing post-treatment values to pre-treatment values for the affected and contralateral arm Proportion of subjects who show a decrease in local tissue water at target sites when comparing post-treatment values to pre-treatment values for the affected side Mean change in perometry and local tissue water post-treatment will be compared for all sites
Skin Changes	
 Proportion of subjects who show a decrease in skin thickness at target site when comparing post-treatment values to pre-treatment values for the affected side Mean change in skin thickness post-treatment will be compared for all sites
Safety	
 Adverse events will be presented in data listings

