Inclusion/Exclusion	
Inclusion Criteria:
 
 Female 18 years of age or older Diagnosis of unilateral breast cancer-related lymphedema Stage I or early Stage II lymphedema without severe fibrosis at the time of enrollment ≥ 5% volume difference between affected and unaffected arm as verified via perometry (LymphaTech 3D scanner) Willing and able to give informed consent Willing and able to comply with the study protocol requirements and all study-related visit requirements 
Exclusion Criteria:
 
 In-home use of pneumatic compression device (PCD) within previous 3 months

	
 2. Therapist or self-administered manual lymph drainage (MLD) within previous 1 week 3. Mastectomy or lymph node removal on side without lymphedema 4. Bilateral lymphedema 5. Heart failure (acute pulmonary edema, decompensated acute heart failure) 6. Acute venous disease (acute thrombophlebitis, acute deep venous thrombosis, acute pulmonary embolism) 7. Active skin or limb infection/inflammatory disease (acute cellulitis, other uncontrolled skin or untreated inflammatory skin disease) on the arms or trunk 8. Active cancer (cancer that is currently under treatment, but not yet in remission) 9. Poorly controlled kidney disease (glomerular filtration rate < 30 mls per minute), hypoproteinemia, pulmonary hypertension, hypothyroidism, cyclic edema, or Munchausen Syndrome 10. Body Mass Index (BMI) >50 11. Any circumstance where increased lymphatic or venous return is undesirable 12. Currently pregnant or trying to become pregnant 13. Allergy to iodine
Treatment Duration	
A single treatment lasting:
 
 • FT-SW: Approximately 40 minutes OR • FT: Approximately 60 minutes
Number Planned	20 subjects randomized (minimum of 10 in each arm) with replacement of up to 5 early withdrawals.

TABLE OF CONTENTS

1.0	Contact Information	7
1.1	Sponsor Contact Information.....	7
1.2	Principal Investigator Information.....	7
1.3	Clinical Investigator Information	7
2.0	Abbreviations	8
3.0	Introduction.....	10
3.1	Background and Rationale.....	10
3.2	Device Description	10
4.0	Study Objective.....	13
5.0	Study Design.....	13
5.1	Endpoints	13
5.2	Subject Selection	14
5.3	Point of Enrollment and Randomization	15
5.4	Treatment Assignment and Duration.....	15
5.5	Study Timeline	15
6.0	Study Assessments.....	15
6.1	Screening/Baseline	16
6.2	Randomization.....	16

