3.2.3 NIRF Imaging

The investigational imaging techniques of near-infrared fluorescence (NIRF) are focused on addressing unmet clinical diagnostic needs in lymphatic imaging through point of care, non-radioactive, clinical imaging diagnostic platform based on image intensifier technology. NIRF imaging has been used under the investigational new drug (IND) experience by the

Principal Investigator (PI) to map lymphatic structure and visualize lymphatic function in hundreds of patients without adverse effects. This method of imaging has shown efficacy in detecting impaired lymphatic function with dermal backflow, defined as abnormal fluorescent signal observed in networks of lymphatic capillaries and/or in the extravascular space, presenting as one of the earliest signs of lymphedema onset (13-15).

NIRF lymphatic imaging provides real-time imaging of the lymphatic anatomy and its function. Following intradermal injections of 25 micrograms of indocyanine green (ICG) in 0.1 cc sterile saline, a dim laser diode light of 785 nm is illuminated on the tissue surface. The light penetrates the tissues and excites the ICG and the resultant fluorescence emanates from tissues and is collected using an intensified camera system.

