4.0 Study Objective

The objective of the study is to demonstrate equivalency in treatment effect, as determined by objective measurements, between the novel simultaneous therapy cycle software and the FDA-cleared FT.

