8.12 NIRF Imaging

After all injections are made and the water content and skin thickness measurements are made, NIRF imaging will commence. From the images of each region, the lymphatic activation (anatomy and propulsion) will be quantified as follows:

- Intact, fluorescent lymphatic vessels observed before and after the treatment will be recorded as an increase in vessels, decrease in vessels, or no change. The two-dimensional, projected area or extent of dermal backflow, before and after treatment, will be quantified using ImageJ (NIH, Bethesda, MD) by adjusting the brightness of the images to 20% of the maximum pixel value and measuring the area of regions of interest drawn around fluorescent areas not associated with intact and well-defined (i.e., “normal”) lymphatic vessels.
- The rate of lymphatic propulsion events observed immediately before and after treatment will be quantified by counting the total number of propulsion events observed and dividing by the total observation time at each region of interest.

Prior to injection and after NIRF imaging is complete, digital photographs of the arms will be acquired. Images of the front and back of the arms will be acquired with the subject standing up and the arms held out away from the sides.

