16.0 Statistical Methods

For continuous variables, descriptive statistics will include the number of subjects (n), mean, standard deviation, median, inter-quartile range, minimum, and maximum, based upon subjects with reported data for the variable being analyzed.

Frequencies (numerator and denominator), percentages, and 95% confidence intervals will be displayed for categorical data. Percentages by categories will be based on the number of subjects with no missing (unreported) data for the specific variable being analyzed and the count of the patients for each individual level of the categorical variable (the level specific numerators). Percentages will add up to 100%, unless otherwise indicated.

There are no plans to impute missing data and there are no plans to explicitly report missing data (counts and/or percentages) in the tables for all variables as part of the planned study report content. Variations in the reported sample sizes within and/or between relevant tables can be used to ascertain insights into unreported data. In some cases, unreported data may be the result of it not being clinically relevant to a particular patient or may represent expected data that was not collected. Selected analyses pertaining to unreported and/or missing data may be discussed and considered as future findings warrant.

The feasibility nature of the study suggests that the statistical focus will be on estimation and hypothesis generation. Thus, formal statistical tests of hypotheses are not planned.

All data processing, summarization, and analyses will be performed using R Version 3.54.0 or higher.

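### One and/or proportion pools a gain in functional vessels with a gain in dermal backflow, a signal the protocol itself calls abnormal, so devices with opposite component effects can show the same result

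*Combined protocol and SAP*

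**What the plan says.** The first outcome under lymphatic activation in Table 1 (section 5.1) is one bullet with one proportion: "Proportion of subjects who show an increase in the number of functional vessels and/or area of dermal backflow per NIRF imaging", comparing post-treatment with pre-treatment values for the affected and contralateral arm.

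Three other places bear on it:

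- Section 3.2.3 (NIRF Imaging) gives the meaning of backflow: "This method of imaging has shown efficacy in detecting impaired lymphatic function with dermal backflow, defined as abnormal fluorescent signal". The same sentence places it among the earliest signs that lymphedema is starting.
- Section 8.12 (NIRF Imaging) measures the two components separately. Vessels "will be recorded as an increase in vessels, decrease in vessels, or no change". Backflow area is obtained by "measuring the area of regions of interest drawn around fluorescent areas not associated with intact and well-defined" vessels, before and after treatment.
- Section 4.0 sets the aim: "The objective of the study is to demonstrate equivalency in treatment effect, as determined by objective measurements". Section 16.0 plans no formal tests and says that "the statistical focus will be on estimation and hypothesis generation".

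For other endpoints Table 1 adds a continuous comparison, for example "Mean change in perometry and local tissue water post-treatment will be compared for all sites", and a similar line for skin thickness. There is no such line for backflow area.

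**The concern.** Read as written, a subject counts as activated if either component rises. A subject who loses vessels and gains backflow is counted. A subject whose backflow shrinks while vessels stay the same is not. Given section 3.2.3, that is hard to interpret: the protocol presents backflow as a marker of impaired function, yet its increase is pooled with an increase in intact vessels and no reason is given. The documents do not settle whether a wider fluorescent area soon after one session is unfavourable or is simply dye that has moved.

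The pooling matters most because the aim is equivalency. An either-or outcome treats its two components alike, so it can hide or shrink a difference between devices and make them look similar, which is the conclusion sought. The absence of formal tests does not remove the problem, because a plan built on estimation needs an estimate with a clear meaning.

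Table 1 also names both the affected and the contralateral arm without saying whether they are reported separately or combined into one count per subject.

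**Working it through.** **Inputs from the documents.** The outcome rule is in Table 1. The synopsis plans 20 randomized subjects, at least 10 per arm. Section 16.0 plans percentages with 95% confidence intervals. No expected rate, margin or power is stated, so there is no figure of the plan's own to reproduce. All rates and counts below are illustrations.

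**1. Limiting case, 10 per arm.** Device A has 5/10 with vessel gain and 0/10 with backflow gain. Device B has 0/10 and 5/10.

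The Wilson 95% interval for 5/10 is 0.237 to 0.763. For 0/10 the lower limit is 0 and the upper limit is z²/(n + z²) = 3.84/13.84 = 0.277. Newcombe's interval for a difference d = p1 - p2 combines these limits:

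- lower = d - √[(p1 - l1)² + (u2 - p2)²]
- upper = d + √[(u1 - p1)² + (p2 - l2)²]

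For vessel gain, d = 0.50:

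- lower = 0.50 - √(0.263² + 0.277²) = 0.50 - 0.38 = 0.12
- upper = 0.50 + √(0.263² + 0²) = 0.76

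| Outcome | A | B | Difference, points (95% CI) |
|---|---|---|---|
| Table 1 proportion | 5/10 | 5/10 | 0 (-37 to 37) |
| Vessel gain | 5/10 | 0/10 | 50 (12 to 76) |
| Backflow gain | 0/10 | 5/10 | -50 (-76 to -12) |

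**2. Less extreme opposite effects.** If the components are independent, the listed proportion is 1 - (1 - v)(1 - q), where v is the probability of vessel gain and q that of backflow gain. Swapping v and q leaves it unchanged:

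- (0.7, 0.1) and (0.1, 0.7) both give 1 - 0.3 × 0.9 = 73%.
- (0.6, 0.2) and (0.2, 0.6) both give 1 - 0.4 × 0.8 = 68%.

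**3. No opposite effects at all.** Let backflow rise at the same rate q on both devices, independently of vessels. The difference in the listed proportion is then (1 - q)(v1 - v2). With v1 = 50% and v2 = 20%, a true 30-point vessel difference appears as follows:

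| q | A | B | Difference shown |
|---|---|---|---|
| 20% | 60% | 36% | 24 points |
| 30% | 65% | 44% | 21 points |
| 50% | 75% | 60% | 15 points |

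Section 8.12 sets no minimum change in area. In limbs with measurable backflow, symmetric measurement error alone would therefore put q near 50% (an assumption).

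**4. How far step 3 depends on independence.** With q equal on both devices, the difference shown is 30 points minus the difference between devices in the share of subjects with both gains. At q = 50%:

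- no overlap gives 100% vs 70%, a difference of 30 points;
- maximal overlap gives 50% vs 50%, a difference of 0 points.

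The shrinkage therefore depends on a quantity that the single proportion does not report.

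**The case against.** The strongest reply has four parts.

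- **Separate reporting may already be implied.** Section 8.12 defines two variables, and section 16.0 gives generic summaries for continuous and categorical data. Applied to those variables, they would yield much of what is wanted. But section 16.0 names no variables, and Table 1, which does name the outcomes, lists only the pooled proportion. The data will exist; the commitment to tabulate them does not.
- **A larger fluorescent area may be a desired acute effect.** Dye is injected at the hand and wrist before treatment (section 8.9), and the endpoint is called activation, not benefit. Section 3.2.3 speaks of detecting disease, not of change after compression. This stands: the direction is unexplained, not shown to be wrong. Even if both increases were favourable, they are different effects, and the pooled count could not show equivalence on either.
- **And/or might loosely mean two measures.** That is possible, but the text is one bullet with one proportion. If two were meant, the wording should say so.
- **The illustrations are constructed.** Exactly opposite responses are unlikely from devices with the same garments and number of therapy cycles (section 3.2.2), and independence is doubtful when both components come from the same images. This also stands. The figures show what the outcome can conceal, not what is expected.

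The missing mean-change line is weak support on its own: propulsion has none either, and vessel change is recorded in categories. The two-arm wording also occurs in the perometry row.

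**Conclusion.** The concern holds. The first lymphatic-activation outcome pools two components in a direction that the protocol does not justify and that sits uneasily with its own description of backflow. Followed literally, it can show no difference where the components differ by 50 points in opposite directions. Under independence and a shared backflow rate of 20% to 50%, it can show a 30-point vessel difference as 24 to 15 points. These sizes rest on assumed rates; what does not depend on them is that the pooled proportion cannot identify the effect on either component.

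The consequence is limited. The study names no primary endpoint, margin or decision rule, plans no test, and has separate propulsion, swelling and skin outcomes. One outcome is affected, not the study as a whole. It should be fixed because it bears directly on the equivalency aim and the remedy is nearly free.

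**What to change.** Replace the pooled bullet in Table 1 with separate outcomes, each reported for the affected arm and for the contralateral arm:

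1. Functional vessels: the proportion with an increase and the proportion with a decrease.
2. Dermal backflow area: the change as a continuous measure, with the proportions increasing and decreasing.

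A cross-tabulation of the two would show subjects whose components move in opposite directions.

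Before analysis, state which direction is regarded as favourable for each component and why, and reconcile that rationale with section 3.2.3. If acute spread of dye is considered a desired effect, report it as its own named outcome.

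The cost is one row of Table 1 and a sentence of rationale. Section 8.12 already collects both components, so no new data or procedures are needed.

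### Propulsion rate and dermal backflow area enter Table 1 only as any-increase proportions, and Section 16.0 plans no FT-SW minus FT difference with an interval for any outcome, although the objective is equivalency

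*Combined protocol and SAP*

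**What the plan says.** Sections 3.1 and 4.0 and the synopsis give the aim as showing that FT-SW and FT are equivalent in treatment effect.

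**Measurement (Section 8.12).** Propulsion is a rate, obtained by "counting the total number of propulsion events observed and dividing by the total observation time at each region of interest". Backflow is an area: "The two-dimensional, projected area or extent of dermal backflow, before and after treatment, will be quantified using ImageJ". Vessels are graded only by direction; they "will be recorded as an increase in vessels, decrease in vessels, or no change".

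**Outcomes (Section 5.1, Table 1).** Lymphatic activation has two outcomes, both proportions of subjects. One counts subjects with an "increase in the number of functional vessels and/or area of dermal backflow per NIRF imaging of the affected and contralateral arm". The other is "Proportion of subjects who show an increase of lymphatic propulsion events immediately after treatment". Swelling has proportions and also a size measure: "Mean change in perometry and local tissue water post-treatment will be compared for all sites". Skin thickness has a matching mean-change line. Lymphatic activation has none.

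**Analysis (Section 16.0).** Continuous variables get n, mean, SD, median, inter-quartile range, minimum and maximum. For the rest, "Frequencies (numerator and denominator), percentages, and 95% confidence intervals will be displayed for categorical data". The stated focus is estimation and hypothesis generation, and no formal tests are planned. The section names no between-arm difference, no interval for one and no equivalence margin.

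**The concern.** An equivalency objective with an estimation focus asks how large the FT-SW minus FT difference is and how uncertain it is. For the first-listed endpoint, the named outcomes record only whether a subject went up. If both devices raise propulsion in nearly every subject, both proportions lie near 100% even when one device raises it far more. Similar percentages could then be read as equivalence. Section 17.0 intends the data for product development and marketing claims, so that reading has consequences.

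The ceiling argument is made for propulsion only. Backflow area has two other problems. Its change can be hidden inside the and/or composite, where a vessel increase alone makes a subject count. Its reading is also unsettled: Section 3.2.3 describes "dermal backflow, defined as abnormal fluorescent signal observed in networks of lymphatic capillaries and/or in the extravascular space", while Table 1 counts an increase in its area towards lymphatic activation.

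**Working it through.** **What can be reproduced.** The planned size is 20 randomized, at least 10 per arm (synopsis). The documents give no margin, SD, effect size, response rate, alpha or power, so this number cannot be re-derived. Everything below is a range under stated assumptions.

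**Precision at 10 per arm.**
- Difference in mean change: half-width = t(0.975, 18 df) × √(2/10) × SD = 2.101 × 0.447 × SD = 0.94 SD of the change.
- Difference in proportions (Newcombe), 10/10 against 10/10: the Wilson lower limit is 10/(10 + 1.96²) = 0.722, so the interval is ±(1 − 0.722) = ±28 points. At 8/10 against 8/10 it is ±34 points.
- With truly equal devices, the whole 95% interval for means lies inside ±m with 50% probability at m = 1.24 SD and with 80% probability at m = 1.53 SD (simulation, 400,000 draws).

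**What the any-increase proportion loses.** Assume normal changes with equal SD, no ties, a mean shift of d SD under FT and f × d SD under FT-SW. The any-increase rates are Φ(d) and Φ(f × d). The share of trials whose 95% interval for the difference excludes zero comes from exact enumeration of 10 against 10 (Newcombe) and from the noncentral t with 18 df (means). It serves here as a yardstick of how well each summary separates the devices.

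| FT shift | FT-SW shift | Any-increase rates | Proportions | Means |
|---|---|---|---|---|
| 1 SD | 0 | 84% / 50% | 33% | 56% |
| 1.5 SD | 0 | 93% / 50% | 57% | 89% |
| 2 SD | 0 | 98% / 50% | 73% | 99% |
| 1 SD | 0.5 SD | 84% / 69% | 9% | 19% |
| 1.5 SD | 0.75 SD | 93% / 77% | 9% | 36% |
| 2 SD | 1 SD | 98% / 84% | 5% | 56% |
| 1 SD | 1 SD | 84% / 84% | 2.3% | 5% |
| 1.5 SD | 1.5 SD | 93% / 93% | 0.3% | 5% |
| 2 SD | 2 SD | 98% / 98% | 0.0% | 5% |

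The first and sixth rows have the same 1 SD gap between devices. Means separate them in 56% of trials both times; proportions fall from 33% to 5% as both rates approach the ceiling. In counts: if FT shows 10/10, the Newcombe interval excludes zero at 6/10 on FT-SW (4 to 69 points) but not at 7/10 (−4 to 60), while a rate of 84% predicts about 8/10.

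The last three rows show that the two columns are not matched on error rate. With equal devices the interval for means excludes zero in 5% of trials and the Newcombe interval less often, so part of the gap is conservatism at n = 10.

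**Counts with ties.** Assume Poisson events, equal viewing time, between-subject CV 0.5 for rate and 0.3 for response, and 10 expected pre-treatment events. If FT triples and FT-SW doubles the rate, the shares are 2% (proportions) and 38% (means). If FT doubles it and FT-SW has no effect, they are 52% and 80%. The pattern is the same.

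**From regions to a subject.** Section 8.12 gives a rate at each region but no rule for combining regions. The choice matters. Take two regions at 2.0 and 0.5 events per minute, neither changing, viewed 5 + 5 minutes before treatment and 8 + 2 after. Pooled, the rate goes from (10 + 2.5)/10 = 1.25 to (16 + 1)/10 = 1.70 per minute, an apparent increase. The within-region changes average to 0.

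**The case against.** The strongest reply is that this is a declared feasibility study with no tests planned, and that at 10 per arm the proposed intervals are also too wide to show equivalency. Both statements are true. The second limits what the fix can deliver. Neither removes the point, since a difference with an interval is estimation, which Section 16.0 names as its focus.

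Several stronger readings are tempting and should be set aside:

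- A reader might infer that the size of the propulsion and backflow changes will go unreported. Section 16.0 sets mean and SD as the general rule for continuous variables, and Section 8.12 makes both measures continuous. If changes are tabulated by arm, an unadjusted interval could be computed from them. What is missing is their naming in Table 1 and the contrast.
- A reader might infer that the limb for propulsion is undefined because that line names none. The endpoint list directly above Table 1 covers the affected and contralateral limb. Only separate scoring of the limbs remains open.
- A reader might take the whole 5% against 56% gap as information lost by dichotomizing. Part of it is Newcombe conservatism, and the share excluding zero behaves like power for a difference, which the plan does not test.
- A reader might infer that Table 1 has the direction of backflow wrong. The documents show two statements that need reconciling, not which is right.

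One practical objection also stands. Keeping every arm, site and probe separate gives up to 24 continuous contrasts: volume 2, tissue water 3 × 2 × 2 = 12, skin thickness 3 × 2 = 6, propulsion 2 and backflow 2. The intervals therefore need a multiplicity caution.

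**Conclusion.** The point holds on the text. Two measures recorded on a continuous scale become named outcomes only by direction, and no outcome has a planned between-arm difference with an interval, despite an equivalency objective and an estimation focus.

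The size depends on assumptions that the documents cannot settle. Under the normal model the loss is moderate if FT-SW does nothing (73% against 99% at a 2 SD FT shift) and large if it works half as well (5% against 56%), with part of each gap due to conservatism. At an FT shift of 1 SD or less and half effect (9% against 19% at 1 SD), the small sample is the main limit for both summaries.

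A reader might conclude that the added intervals would let the trial demonstrate equivalency. The documents do not support that: they state no margin, and a half-width of 0.94 SD requires a large one. The region rule and the reading of backflow are clarifications. This is a change that should be made, at little cost, and it leaves the no-testing stance intact.

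**What to change.** **Table 1**
- Add mean change in propulsion rate and mean change in dermal backflow area as continuous outcomes, separately for the affected and contralateral arm.
- Report backflow area on its own as well as in the composite.
- Compute changes within regions imaged at both times and combine them by one rule fixed before unblinding, for example an equal-weight average for rate and a sum for area.
- Reconcile the description of backflow in Section 3.2.3 with the direction counted in Table 1, and state before unblinding how a rise or fall in area will be read.

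**Section 16.0**
- Report the FT-SW minus FT difference with a 95% confidence interval for the Table 1 continuous outcomes and proportions (Newcombe, for example, for proportions), labelled descriptive and unadjusted for multiplicity.
- Keep the any-change proportions as supportive.
- State that at 10 per arm the half-width is about 0.94 SD for means, and ±28 points for proportions even at 10/10 against 10/10, so that the intervals cannot by themselves demonstrate equivalency unless the margin is large.

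**Cost.** Wording and a little code; all data are already collected. An equal-weight average gives a briefly viewed region the same say as a long one, so noise may rise slightly. The wide intervals will show the limits of the sample openly.

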6.3 Treatment

The randomized treatment assignment will be administered to the affected limb. The personnel administering the treatment will not perform any study assessments as they will be unblinded to the treatment.

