8.10 MoistureMeterD Measurements

Local tissue water (LTW) measures will be obtained using the FDA-cleared MoistureMeterD™ (MMD) with the M25 (2.5 mm) and L50 (5.0 mm) probes (Delfin Technologies, Finland). This non-invasive, rechargeable, battery-operated device and technology has been demonstrated to provide a measure of LTW and its change based on measurements of the skin's tissue dielectric constant at a frequency of 300 MHz. The method has been widely used in clinical studies as a highly sensitive measurement of water content and edema in the skin and subcutis (16-19). There are no risks associated with the use of this data collection device. In addition, data collected from this device will not be used in the diagnosis or treatment of lymphedema.

The MMD measurements will be performed on the affected and unaffected side before and after treatment. Measurements may only be conducted by research personnel with documented training showing the individual was able to independently and accurately conduct the measurements.

The following measurement procedures will be followed to assess the upper extremity tissue dielectric constant (TDC) values as indices of skin/tissue water:

- Ensure the subject remains in a seated position with the arms relaxed
- Turn on the MoistureMeter D unit, select the correct probe size on the display, and wait for the word “wait” to disappear from the display before taking any measurements.
- Measure and record the TDC values at sites A, B, and C (See Figures 3-5) by firmly placing the probe on the marked site such that the entire probe depresses the skin and leaves a slight indentation.
- All measurements will be made in duplicate using the L50 (5 mm) probe alternating in a consistent fashion (A, B, C, A, B, C) to ensure tissue water is not displaced at the time the second measurement is taken.
- Clean the L50 probe with an antiseptic cleansing towel or ethanol and return to the storage case.
- Repeat steps 1 through 5 (in duplicate) using the M25 (2.5 mm) probe.
- Turn off the MoistureMeterD unit, clean the M25 probe with an antiseptic cleansing towel or ethanol, and return both the probe and MoistureMeterD unit to the storage case.

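### Table 1 promises a comparison of mean changes, but Section 16 plans no FT-SW minus FT difference for any outcome and no confidence interval for any continuous outcome

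*Combined protocol and SAP*

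**What the plan says.** Section 4.0 gives the objective as "to demonstrate equivalency in treatment effect, as determined by objective measurements". Section 5.1 frames the endpoints as a comparison of FT with FT-SW after one treatment. For swelling, Table 1 says: "Mean change in perometry and local tissue water post-treatment will be compared for all sites". It says the same of mean change in skin thickness. The other efficacy measures in Table 1 are proportions of subjects who changed in a given direction.

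Section 16.0 says: "For continuous variables, descriptive statistics will include the number of subjects (n), mean, standard deviation, median, inter-quartile range, minimum, and maximum". For categorical outcomes it says: "Frequencies (numerator and denominator), percentages, and 95% confidence intervals will be displayed for categorical data". It rules out formal hypothesis tests because "the statistical focus will be on estimation and hypothesis generation". It names no between-arm difference, no interval for a continuous variable or its change, and no use of the pre-treatment value. No other section supplies these.

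On what is measured: "The randomized treatment assignment will be administered to the affected limb" (Section 6.3), and both arms of each subject are assessed. For tissue water, Section 8.10 says "Measure and record the TDC values at sites A, B, and C" with the 5 mm probe in duplicate, then "Repeat steps 1 through 5 (in duplicate) using the M25 (2.5 mm) probe". Section 8.11 measures skin thickness at the same three sites. Section 8.12 quantifies dermal backflow area and propulsion rate as numbers, but Table 1 carries them forward only as proportions with an increase.

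**The concern.** In a two-arm study whose stated focus is estimation, the quantity of interest is the difference between the arms, with its uncertainty. The plan stops one step short and describes each arm's results. Two columns of means, or two percentages each with its own interval, do not show how large a difference between the devices the data leave open.

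The objective makes this matter. At 10 per arm, results that look alike can be taken as support for equivalency when the data are also compatible with a large difference. Section 17.0 foresees use of the data in product development and marketing, with no publication planned, so outside readers are unlikely to correct such a reading. The missing interval would not prove equivalence, since no margin is stated, but it would show which differences have not been excluded.

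**Working it through.** **Inputs.** From the documents: 20 subjects randomized 1:1, at least 10 per arm (Synopsis, Section 5.4). The documents give no SD of change, response rate, pre/post correlation or margin, and no power or precision figure to reproduce. Widths for means are therefore in units of the SD of change; response rates and correlations are assumed over a range.

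**1. Difference in mean change.** The 95% half-width is t(0.975, n1+n2−2) × √(1/n1 + 1/n2) × SD of change.
- 10 v 10: 2.101 × 0.447 = 0.94 SD.
- 8 v 8 (assumed): 2.145 × 0.500 = 1.07 SD.
- 10 v 7 (assumed): 2.131 × 0.493 = 1.05 SD.

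The smaller numbers are plausible for skin thickness, because Section 8.11 leaves scans with an unclear border unmeasured.

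**2. Difference in proportions.** The Newcombe interval combines the two Wilson intervals. With the same proportion p in both arms and Wilson limits L and U, its half-width is √[(p−L)² + (U−p)²].
- 5/10 in each arm: L = 0.237, U = 0.763; √(0.263² + 0.263²) = 0.373, or 37 points.
- 8/10 in each arm: L = 0.490, U = 0.943; √(0.310² + 0.143²) = 0.341, or 34 points.
- 9/10 in each arm: L = 0.596, U = 0.982; √(0.304² + 0.082²) = 0.315 (0.31504 before rounding), or 32 points.

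For comparison, the interval Section 16.0 does plan for a single arm at 8/10 is 44% to 97% (Clopper-Pearson; the document names no method).

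**3. Adjusting for the pre-treatment value.** With equal pre and post variance and correlation ρ, the ratio of the ANCOVA variance to the change-score variance at 10 per arm is (1+ρ)/2 × 17/16. This gives 0.797, 0.903, 0.956, 1.009 and 1.036 at ρ = 0.5, 0.7, 0.8, 0.9 and 0.95. Simulated ratios of mean interval width are 0.895, 0.952, 0.981, 1.007 and 1.020, with coverage of 0.949 to 0.951. ANCOVA is thus about 10% narrower to 2% wider.

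**4. Imaging measures.** Backflow area may be skewed. In simulations with assumed lognormal areas (log-SD 0.5 to 1.5, ρ 0.5 to 0.95), the Welch interval for the difference in change covers 0.955 to 0.981 with no true difference. With a 1.5-fold difference it covers 0.853 to 0.955, against 0.777 to 0.945 for ANCOVA. For assumed Poisson propulsion counts (mean 1 to 6), Welch covers 0.938 to 0.957 and ANCOVA 0.924 to 0.954. Welch is the safer of the two here, but not fully safe under strong skew.

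**5. Number of mean-difference intervals.** Per limb: volume 1, tissue water 3 sites × 2 probes = 6, skin thickness 3, backflow area 1, propulsion rate 1; total 12. Both limbs: 24. Expected to miss the true value: 0.05 × 24 = 1.2.

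**The case against.** The strongest reply is that the plan already supplies most of what is needed. Section 5.1 compares FT with FT-SW and makes mean change an outcome; Section 16.0 gives n, mean and SD for whatever variable is analysed. The natural reading is that n, mean and SD of change appear by arm, from which anyone can compute the unadjusted interval. That stands. A reader might infer from Section 16.0's silence on arms and change scores that no interval could ever be recovered; the documents do not support that inference. What remains is that the interval is not a planned result, and that a baseline-adjusted one cannot be recovered from such a table.

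Second, the planned intervals on percentages already show severe imprecision, as 44% to 97% does. This also stands, so it would be wrong to say that the plan shows no precision for the proportions. These intervals describe one arm each, however, not the difference.

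Third, this is a feasibility study that openly plans no tests, and Section 16.0 says the statistics will include its list, which does not exclude others. A reader might take the absence of tests as the fault. It is not: it is a declared choice, and nothing here asks for a test, a margin or more subjects. But a focus on estimation is a reason to plan the estimated difference, not to omit it.

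Fourth, ANCOVA may seem a matter of taste, since the documents give no correlation and the gain may be nil. It is fair that the gain is uncertain. The cost is at most about 2% in width over the range examined, and the pre-treatment value is already collected.

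**Conclusion.** The concern holds. The plan aims at equivalency and promises a comparison of mean changes, but specifies no between-arm difference for any outcome and no confidence interval for any continuous outcome. If it is followed as written, similar arms could be read as equivalent while differences of up to 0.94 SD of change, or 32 to 37 percentage points, remain open.

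These sizes assume 10 evaluable subjects per arm, roughly normal changes with a common SD, identical observed results in the two arms, and observed proportions between 5/10 and 9/10. At an assumed 8 v 8 the figure for means rises to 1.07 SD. The harm is limited, because an unadjusted interval could probably be rebuilt from the by-arm summaries. Nor should a reader infer that adding intervals would turn the study into a demonstration of equivalence: without a margin they only describe. The change should be made, but the trial can run as designed without it.

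**What to change.** Add to Section 16.0:

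- Summaries of change from pre-treatment are presented by arm, with n, mean and SD of change.
- For limb volume, tissue water (by site and probe, duplicates averaged) and skin thickness (by site), one FT-SW minus FT difference in mean change with a 95% confidence interval, adjusted for the pre-treatment value by ANCOVA. The affected limb comes first; the contralateral limb is secondary.
- For the change in backflow area and in propulsion rate (Section 8.12), combined over regions within each limb, one prespecified Welch between-arm difference with a 95% interval, noting that it may under-cover if area is strongly skewed.
- For each Table 1 proportion, a Newcombe 95% interval for the between-arm difference, as supportive.
- All intervals are labelled descriptive, not adjusted for multiplicity, and not a demonstration of equivalence because no margin is stated.

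The cost is a few sentences and a few lines of R, with no new data and no change in sample size. The report gains 12 mean-difference intervals per limb, 24 for both, of which about 1.2 would be expected to miss the true value. The proportion differences come on top: up to 12 for the affected limb if sites and probes are kept separate (vessels and/or backflow 1, propulsion 1, volume 1, tissue water 6, skin thickness 3). ANCOVA uses one degree of freedom and changes interval width by about −10% to +2% over assumed correlations of 0.5 to 0.95.
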